3.4.3 Exploratory objectives

Exploratory objectives are

- to compare immunogenicity (geometric mean titer [GMT]) of nOPV2 candidate 1 and nOPV2 candidate 2 in healthy OPV-vaccinated adults, with historical control of Sabin OPV2 (study UAM1);
- to assess immunogenicity (geometric mean titer [GMT]) of nOPV2 candidate 1 and nOPV2 candidate 2 in healthy IPV-only vaccinated adults;
- to compare viral shedding following nOPV2 candidate 1 or nOPV2 candidate 2 administration in a pre-specified subset of stool samples in healthy OPV-vaccinated adults, with historical control of Sabin OPV2 (study UAM1);
- to assess viral shedding following nOPV2 candidate 1 or nOPV2 candidate 2 administration in a pre-specified subset of stool samples in healthy IPV-only vaccinated adults;

The shedding analyses may initially be conducted using a subset of samples in the 10 days following administration of each dose (e.g. day 0, 3, 5, 7, and 10) and all samples at day 14 and thereafter. The remaining samples will be stored pending evaluation of the initial analyses; PCR and CCID₅₀ will be conducted on these stored samples if deemed important for the complete interpretation of the study results.

Exploratory objectives will also include comparison of neurovirulence (as measured in animal model(s)) and assessment of the genetic stability via analysis of genetic sequence, including but not limited to the modified regions of shed virus in a subset of stool samples of all OPV-vaccinated adults, relative to historical control of Sabin OPV2.

Exploratory objectives will also include assessment of neurovirulence (as measured in animal model(s)) and the genetic stability via analysis of genetic sequence, including but not limited to the modified regions of shed virus in a subset of stool samples of all IPV-only vaccinated adults given doses of nOPV2 candidates 1 and 2.

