6.7.1 Exploratory Viral Shedding Endpoints

Throughout, viral shedding analyses will be conducted by group and dose number. The descriptive summaries below will also be computed separately by site. Between-group inferential analyses will additionally be conducted among the site in common between UAM1 and UAM4, for OPV-vaccinated subjects, if the post-dose-1 between-site GMT comparison indicates a significant difference in immunogenicity between sites. The shedding analyses will be conducted considering all available samples, collected at Days 0-10, 14, 21, 28, and 42 following each dose (with day of vaccination defined as Day 0) and additional samples collected, as necessary, to define the end of shedding for participants. All viral shedding data will be listed, including both sample collection and assay results.

Categorical summaries of type 2 viral shedding positivity (positive via PCR) and continuous summaries of viral titers (\log_{10} CCID₅₀/g among both shedders and shedders/non-shedders combined) will be produced by group and by post-vaccination day. Each of these will be augmented with two-sided 95% confidence intervals. The Clopper-Pearson exact method will be used for shedding positivity rate, and the bootstrap method (10,000 replicates, quantile method) will be used for the median \log_{10} viral titers. Subjects who are PCR-negative for viral shedding at a given time point will be assigned the value of 0 for computations involving the \log_{10} CCID₅₀/g, and values PCR positive for type 2 poliovirus but below LLOQ ($2.75 \log_{10}$ CCID₅₀/g) or above ULOQ ($8.25 \log_{10}$ CCID₅₀/g) will be assigned the corresponding value of LLOQ or ULOQ.

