For each subject, the extent of viral shedding will be calculated as the area under the curve (using the linear trapezoidal method) of \log_{10} -transformed values of viral concentration in stool samples as determined using quantitative PCR (viral identity) and CCID₅₀ (titer) from samples taken through 28 days following each vaccine dose, and this continuous variable will be summarized. If a subject is missing two consecutive shedding data points among those intended to be tested for this computation due to samples not provided and/or unevaluable samples, the subject will have a missing value. This requirement regarding consecutive missing samples may be relaxed at the analysis stage if sample size for this computation is significantly impacted. Additionally, the Sheding Index Endpoint (SIE) will be computed as the arithmetic mean of \log_{10} CCID₅₀/g obtained from Days 7, 14, 21, and 28. Here, a single missing daily value will lead to a missing

SIE value, although windows of +/- 2 days will be applied to sample availability. If samples are available at both +1 (+2) and -1 (-2), then the mean \log_{10} CCID₅₀/g from these two days will be used for this computation. This will be summarized as a continuous variable using the same methods for daily viral shedding described above.

Additionally, a summary of time-to-shedding-cessation will be prepared using Kaplan-Meier methods. The day of cessation of shedding will be defined as the day of the first sample negative for shedding after which the following two samples are also negative. Summaries will be produced using Kaplan-Meier methods, and will include quartiles and corresponding 95% confidence intervals, as well as the estimated shedding rate at study days 3, 5, 7, 10, 14, 21, and 28 with corresponding 95% confidence intervals. Subjects who are positive for type 2 viral shedding at their last available assessment date with an evaluable stool sample, or who fail to cease shedding prior to a 2nd dose will be right-censored at the last time point they were known to be shedding virus. The time-to-shedding-cessation curves will be displayed graphically, and the comparison of the difference in time to shedding cessation curves between candidate groups in study M4 and corresponding controls subjects from study UAM1 will be conducted by computing the two-sided log-rank p-value.

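### The missing-sample rule for the shedding AUC counts stools, not days: a 3-day gap is voided, a 14-day gap is kept, and the rule may be loosened at analysis without a stated limit

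*SAP*

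**What the plan says.** All references are to SAP 6.7.1 unless stated.

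- Sampling: "The shedding analyses will be conducted considering all available samples, collected at Days 0-10, 14, 21, 28, and 42 following each dose".
- Measure: the extent of shedding is "calculated as the area under the curve (using the linear trapezoidal method"), using values "from samples taken through 28 days following each vaccine dose". That gives 14 nominal points: Days 0-10, 14, 21 and 28.
- Exclusion: the AUC is missing "If a subject is missing two consecutive shedding data points among those intended to be tested for this computation", because the stool was not provided or could not be evaluated. No maximum gap in days is set.
- Escape clause: "This requirement regarding consecutive missing samples may be relaxed at the analysis stage if sample size for this computation is significantly impacted".
- Use: in OPV-vaccinated subjects, the difference in median AUC from UAM1 is given with a bootstrap 95% interval.

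SAP 3.4.3 adds that "The shedding analyses may initially be conducted using a subset of samples in the 10 days following administration of each dose", with Days 0, 3, 5, 7 and 10 as an example. Protocol 2.3 gives Days 0, 3, 7 and 10.

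**The concern.** Two adjacent missing points mean very different things at different places on this schedule. Early on they cost two days of daily sampling; later, a single point stands for a week or more. A rule that counts points can therefore drop a subject with a short gap and keep one with a long gap.

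The escape clause adds a second problem. It does not say how large a loss triggers it, what rule would replace the present one, or when and by whom the decision is taken. The OPV groups are single-blind (SAP 3.6) and UAM1 was run in 2015-2016 (SAP 5.1), so the comparison could already be known when the choice is made. At stake are which subjects enter the AUC comparison with UAM1, and whether that set is fixed in advance.

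**Working it through.** The plan states no sample size, power or missing-stool rate for the AUC, so there is no figure to reproduce.

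**Step 1. Gaps and weights.** The trapezoid weight of an interior point is (next day − previous day)/2. On the 14 nominal days this gives 0.5 for Day 0, 1 for each of Days 1-9, 2.5 for Day 10, 5.5 for Day 14, 7 for Day 21 and 3.5 for Day 28, in total 28.

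| Missing | Gap bridged | Weight of 28 | Present rule |
|---|---|---|---|
| any pair from (1,2) to (8,9) | 3 days | 2 (7.1%) | void |
| Days 9, 10 | 6 days | 3.5 (12.5%) | void |
| Days 10, 14 | 12 days | 8 (28.6%) | void |
| Day 14 only | 11 days | 5.5 (19.6%) | keep |
| Day 21 only | 14 days | 7 (25.0%) | keep |
| Days 14, 21 | 18 days | 12.5 (44.6%) | void |
| Days 21, 28 | tail after Day 14 lost | 10.5 (37.5%) | void |

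A subject voided only for a pair from (1,2) to (8,9) has a largest gap of 7 days, the same as a fully sampled subject. With the reduced test sets, the shortest interior gap that voids is 7 days (0, 3, 5, 7, 10) or 10 days (0, 3, 7, 10), still below the 14 days accepted for Day 21.

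**Step 2. Weight is not error.** Write y for the log10 titre on a day; SAP 6.7.1 scores PCR-negatives as 0 and positives below the limit of quantitation as 2.75. Bridged area minus full-grid area is:
- Day 21 missing: 7 × [(y14 + y28)/2 − y21].
- Days 8 and 9 missing: y7 + y10 − y8 − y9.
- Days 9 and 10 missing: 2.5·y8 + y14 − y9 − 2.5·y10.

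A subject at 2.75 on Day 14 and negative afterwards gains 3.5 × 2.75 = 9.6 when Day 21 is lost. A subject negative on Days 14, 21 and 28 gains 0. A subject at 2.75 on Day 8 and negative afterwards gains 2.5 × 2.75 = 6.9 when Days 9 and 10 are lost. So an early pair can matter more than Day 21 for a short shedder.

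**Step 3. Share of subjects affected.** All 2^14 missing patterns were enumerated, with stools missing independently at an assumed rate m.

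| m per stool | 5% | 10% | 15% | 20% |
|---|---|---|---|---|
| Voided, present rule | 3.1% | 11.4% | 23.2% | 36.8% |
| Voided, interior gaps up to 7 days re-admitted | 1.0% | 3.8% | 8.2% | 14.1% |
| Voided, interior gaps up to 3 days re-admitted | 1.3% | 5.3% | 11.8% | 20.6% |

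At m = 10%, 7.2% of all subjects are voided although no gap exceeds 7 days, while 14.8% are kept with a gap of 11 days or more. Over m = 2% to 20%, 83% to 70% of voided subjects have a largest gap under 14 days; the other 17% to 30% do not.

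**Step 4. Precision.** As a rough guide, interval width grows by 1/√(1 − loss). Under the present rule this is 1/√0.969 = 1.02 at m = 5%, 1/√0.886 = 1.06 at 10% and 1/√0.632 = 1.26 at 20%. With the 7-day limit it is 1/√0.962 = 1.02 at 10% and 1/√0.859 = 1.08 at 20%.

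**The case against.** The case for leaving the rule alone has four parts.

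- **It removes bad patterns too.** Pairs (14,21) and (21,28) are the worst covered, and they are voided. This stands. A reader might infer from the Day 8-9 and Day 21 contrast that the rule discards the better-measured subjects in general. The enumeration does not support that: most voided subjects have no gap of 14 days or more, but 17% to 30% do.
- **Protecting the early daily samples is defensible.** This stands in part. Step 2 shows that losing Day 21 costs nothing once a subject is negative. The documents give no shedding rates from which to say how common that is.
- **The relaxation is conditional and would be visible.** Its trigger is a count of evaluable subjects, not a result; SAP section 2 requires changes to be amended before lock or documented in the reports; and the AUC values are listed. A reader might infer that the sponsor expects heavy loss or means to choose by result. The text says neither. What remains is that no threshold or replacement rule is stated and nothing keeps the decision ahead of the results.
- **The impact is limited.** The AUC is exploratory and stands beside daily positivity, daily titres, the shedding index and time to cessation. The index is already missing when Day 21 has no sample within 2 days. UAM1 has the same stool schedule through Day 28. This stands and limits the priority.

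**Conclusion.** The inconsistency holds exactly on the nominal schedule: 3 days and 7% of weight voided, 14 days and 25% kept. The open-ended relaxation is a separate weakness and would need closing even if the gap rule were left alone.

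The size depends on missing-stool rates that the documents do not give, and on independence between stools, which is also assumed. At 5% missing per stool the loss is 3.1% of subjects and hardly matters; at 10% to 20% it is 11.4% to 36.8%. The precision figures are only a rough guide for a bootstrap difference in medians when many values are 0. The 3-day figure assumes that all daily stools are tested, as SAP 6.7.1 says.

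A reader might go further and accept any gap up to 14 days, since that is what a missing Day 21 leaves, or score a missing Day 0 stool as 0. Neither is supported. A 14-day limit would keep a subject with no stool on Days 1-10 (9 × 1 + 2.5 = 11.5 of 28 days, 41%), whom the present rule voids. Scoring Day 0 as 0 would conflict with SAP 5.3, which rules out imputing results, and the schedule does not mark the Day 0 stool as collected before vaccination.

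Priority: low to moderate, because the endpoint is exploratory.

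**What to change.** Before database lock, amend SAP 6.7.1 as follows.

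1. Keep the rule on two consecutive missing points, with one exception: do not void the AUC when the missing run is interior and the evaluable samples on either side are at most 7 nominal days apart. Seven days is the largest gap in the full schedule. A tighter limit, such as 3 days within Days 0-10, is also acceptable. Use nominal days, because the Day 28 stool is collected 1 or 2 days before Visit 4.
2. Leave the handling of Day 0 and of the end of the window unchanged, with no imputation of Day 0.
3. Apply the rule identically to UAM1 and UAM4.
4. Delete the sentence allowing relaxation at the analysis stage.
5. Report the AUC under the present rule as a sensitivity analysis.

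The cost is SAP wording and a few lines of code. Because the change only re-admits subjects, everyone now kept stays in. The downside is interpolation error in those re-admitted, largest if the gap falls at peak shedding. At the 7-day limit a run of six daily stools could be bridged (6 of 28 days, 21%, still below the 25% of Day 21), and the limit applies to each run, so several can add up. The 3-day limit bridges only two daily stools per run, at the price of re-admitting fewer subjects.

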Administration of vaccine ^j	X				
Serum sample for polio antibodies	X ^e			X	
Stool sample for viral culture/quantitative PCR, stool sample for potential poliovirus sequencing, stool sample for potential neurovirulence assay ^l	X-----X ^l		X	X ^l	X
Solicited systemic AEs (Diary) ^k	X-----X				
Remote contact for safety follow-up ^m					
Concomitant therapies ⁿ	X	X	X	X	X
Adverse events ⁿ	X	X	X	X	X
Reminder Code of Conduct ^o	X	X	X	X	X

- a. In case of early termination, the subjects will be asked to return to the clinical site within 14 days after discontinuation for assessments as outlined on Day 28.
- b. No study-related assessment is to be carried out before signing of the informed consent form.
- c. Including polio vaccination history.
- d. Includes weight and height at Day 0. After Day 0, symptom-directed physical examination.
- e. Prior to vaccination.
- f. Blood pressure and heart rate (supine) and oral body temperature. On Day 0, vital signs will be assessed prior to and 30 min after vaccination.
- g. For a list of assessments, please see Appendix 1: Overview of Laboratory assessments.

- h. In women of childbearing potential, a urine pregnancy test will be performed.
- i. Includes HBsAg, anti-HCV and anti-HIV antibodies, and IgA.
- j. The subjects will be kept under medical supervision for at least 30 min after vaccination.
- k. Solicited AEs will be collected for Days 0-7.
- l. Subjects will be asked to collect the first stool of every day in the provided container and to store this in the provided thermal bag with cooling elements: daily collection on Days 0 to 10 plus collection on Days 14, 21, V4 minus 1 or 2 days and V5 minus 1 or 2 days. At Day 0 the storage procedure will be explained and the collection material provided. Subjects who are still shedding virus in one of the 3 last stool samples will be asked to further collect 3 consecutive stool samples every 3 weeks till end of shedding.
- m. Remote contact (text message by sms, WhatsApp or email) on Day 3 and on Day 21 for safety follow-up and reminder stool collection scheme.
- n. Adverse events and intake of concomitant medication(s) will be monitored continuously from informed consent until the last study-related activity. The subjects can record unsolicited AEs on their diary card.

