- l. Subjects will be asked to collect the first stool of every day in the provided container and to store this in the provided thermal bag with cooling elements: after each vaccine dose, daily collection on Days 0 to 10 plus collection on Days 14, 21, V4 minus 1 or 2 days (= V7 minus 1 or 2 days after 2nd vaccination) and V8 minus 1 or 2 days. At Day 0, the storage procedure will be explained and the collection material provided. Subjects who are still shedding virus in one of the 3 last stool samples will be asked to further collect 3 consecutive stool samples every 3 weeks till end of shedding.
- m. Remote contact (text message by sms, WhatsApp or email) on Day 3 and on Days 21, 31 and 49 for safety follow-up and reminder stool collection scheme.
- n. Adverse events and intake of concomitant medication(s) will be monitored continuously from informed consent until the last study-related activity. The subjects can record unsolicited AEs on their diary card.
- o. After signing on screening visit, weekly reminder Code of Conduct by email or sms and on each visit to emphasize the need and importance of hygienic measures and respecting the inclusion/exclusion criteria until end of study.

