- b. No study-related assessment is to be carried out before signing of the informed consent form.
- c. Including polio vaccination history.
- d. Includes weight and height at Day 0. After Day 0, symptom-directed physical examination.
- e. Prior to vaccination.
- f. Blood pressure and heart rate (supine) and oral body temperature. On Day 0, vital signs will be assessed prior to and 30 min after vaccination.
- g. For a list of assessments, please see Appendix 1: Overview of Laboratory assessments.
- h. In women of childbearing potential, a urine pregnancy test will be performed.
- i. Includes HBsAg, anti-HCV, and HIV antibodies.
- j. The subjects will be kept under medical supervision for at least 30 min after vaccination.
- k. Solicited AEs will be collected for Days 0-7.
- l. Subjects will be asked to collect the first stool of every day in the provided recipient and bring the samples with them at the next scheduled visit. Daily collection on Days 0 to 10 plus collection on Days 14, 21 and V4 minus 1 or 2 days. Stool samples need to be stored by the subject at 4-8°C for maximum 7 days, before brought to the vaccine center. At Day 0 the storage procedure will be explained and the collection material provided.
- m. Daily remote contact (text message by sms, WhatsApp or email) from Day 0 to Day 10 and also on Day 21 and 42.

- n. Adverse events and intake of concomitant medication(s) will be monitored continuously from informed consent until the last study-related activity. The subjects can record unsolicited AEs on their diary card.

TIME AND EVENTS SCHEDULE – GROUP 2

Assessments	Group 2							Follow-up contact
	1	2	3	4	5	6	7	
Time of Visit (days)	D 0	D 7 (+/- 2D)	D 14 (+/- 3D)	D 28 (+/- 2D)	D 35 (+/- 2D)	D 42 (+/- 3D)	D 56 ^a (+/- 2D)	D 70 (+/- 4D)
Visit Window								
Informed consent ^b	X							
In-/exclusion criteria	X							
Medical history/concomitant diseases	X							
Medication history ^c	X							
Demographic data	X							
Physical examination ^d	X ^e	X		X ^e	X			X
Vital signs ^f	X ^{e,f}	X		X ^e	X			X
Clinical laboratory tests ^g	X ^e	X		X ^e	X			X
Pregnancy test ^h	X			X ^e				
Serology ⁱ	X							
Randomization	X							
Administration of vaccine ^j	X			X				
Serum sample for polio antibodies	X ^e			X ^e				X
Stool sample for viral culture/quantitative PCR ^l , stool sample for potential poliovirus sequencing, stool sample for potential neurovirulence assay	X----- X ^l	X	X----- X ^l		X			
Solicited systemic AEs (Diary) ^k	X----- X		X----- X					

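### The SAP's ±2-day window for the Day 28 component of the Shedding Index does not match the protocol's stool schedule, so a compliant subject can lose the whole index

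*SAP*

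**What the plan says.** SAP 6.7.1 defines the SIE as the arithmetic mean of log10 CCID50/g "obtained from Days 7, 14, 21, and 28". The missing-value rule is strict: "Here, a single missing daily value will lead to a missing" index. The only allowance comes next: "SIE value, although windows of +/- 2 days will be applied to sample availability". Days are counted "with day of vaccination defined as Day 0". The same section lists the collection days as 0–10, 14, 21, 28 and 42, and computes the AUC from samples up to 28 days after each dose.

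The protocol does not fix a stool to Day 28. In the Section 8.1 schedule for Groups 1 and 3, footnote l asks for a stool every day up to Day 10, "plus collection on Days 14, 21, V4 minus 1 or 2 days and V5 minus 1 or 2 days", with Visit 4 at Day 28 ±2. For the two-dose groups, footnote l has "V4 minus 1 or 2 days (= V7 minus 1 or 2 days after 2nd vaccination) and V8 minus 1 or 2 days", with Visit 7 at Day 56 ±2. The UAM1 control used the same rule after dose 1 (Appendix 3): "Daily collection on Days 0 to 10 plus collection on Days 14, 21 and V4 minus 1 or 2 days", with the same ±2-day window on Visit 4.

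**The concern.** The analysis window is centred on Day 28, while the collection rule is centred 1 or 2 days before a visit that can itself be early. The two do not line up, and the all-or-nothing rule turns one badly placed sample into a missing index. Subjects who followed the protocol exactly would drop out of the SIE comparison with UAM1, which SAP 6.7.1 reports with bootstrap 95% confidence intervals. The AUC has a milder version of the problem at its upper limit. What is at stake is precision and, for the AUC, curves that cover different lengths of follow-up.

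**Working it through.** The plan gives no figure for this point, so there is nothing to reproduce first.

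**Inputs**
- SIE window for Day 28: Days 26–30. For Day 21: Days 19–23 (SAP 6.7.1).
- Visit 4 (V4) on Days 26–30; Visit 7 (V7) on Days 54–58; stool taken k = 1 or 2 days before (Protocol 8.1).
- Assumed, because the documents are silent: three distributions of visit day over −2, −1, 0, +1, +2 days. A is 20% on each day; B is 10/10/60/10/10%; C is 5/10/70/10/5%. Also assumed: k = 1 and k = 2 equally likely, and visit days independent.

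**After dose 1.** Stool day = V4 − k.

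| V4 | k = 1 | k = 2 |
|---|---|---|
| 26 | 25, out | 24, out |
| 27 | 26, in | 25, out |
| 28 | 27, in | 26, in |
| 29 | 28, in | 27, in |
| 30 | 29, in | 28, in |

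Three of 10 compliant combinations fall outside. Loss = P(V4 = 26) + ½P(V4 = 27):
- A: 0.20 + 0.10 = 30%
- B: 0.10 + 0.05 = 15%
- C: 0.05 + 0.05 = 10%
- every V4 on Day 28 or later: 0%

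**Pooled post-dose-1 comparison.** SAP 6.7 pools one- and two-dose groups, 50 + 50 per candidate. Two-dose subjects also give a stool on the day of dose 2, which the UAM4 schedule marks as taken before vaccination. With V4 in window it falls on Days 26–30. If it is used, pooled loss = ½ × one-dose loss + ½ × 0 = 15%, 7.5% or 5%.

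**After dose 2, V7 timed from dose 2.** The table above applies again: 30%, 15% or 10%.

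**After dose 2, V7 timed from Day 0.** Put x = (V7 − 56) − (dose-2 day − 28). Stool day after dose 2 = 28 + x − k, ranging from 54 − 2 − 30 = 22 to 58 − 1 − 26 = 31. It is outside if x ≤ −2, if x = −1 with k = 2, or if x = 4 with k = 1. Loss = P(x ≤ −2) + ½P(x = −1) + ½P(x = 4):
- A: 6/25 + 2/25 + 0.5/25 = 34% (17 of 50 combinations: 16 early, 1 late)
- B: 0.16 + 0.07 + 0.005 = 23.5%
- C: 0.0925 + 0.075 + 0.00125 = 16.9%

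This leaves out postponed second doses. Protocol 5.4 allows up to 7 days' delay and does not say whether V7 moves with it. With dose 2 on Day 35 and V7 unmoved, the stool falls 54 − 2 − 35 = 17 to 58 − 1 − 35 = 22 days after dose 2.

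**AUC, one-dose subjects.** Only V4 = 30 with k = 1 gives a stool after Day 28 (Day 29). A single missing point does not trigger the rule on two consecutive missing samples, so the AUC is kept but stops at Day 21, 7 of 28 days short. Share = ½P(V4 = 30): A 10%, B 5%, C 2.5%.

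**Windows proposed below.** After dose 1, Days 24–30 take in all 10 combinations and do not touch the Day 21 window. After dose 2, Days 24–31 take in everything if V7 is timed from dose 2. If V7 is timed from Day 0, Days 22–23 stay outside: P(x = −4) + ½P(x = −3) = 8% (A), 2% (B) or 0.75% (C).

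**The case against.** The strongest reply is that Day 28 in the SAP is a nominal label, so whatever stool precedes Visit 4 is the Day 28 value and nothing is lost. The SAP's list of collection days gives this some support. But the SAP counts from the day of vaccination, sets a window in days, and averages samples lying one or two days either side of the target. That is the language of actual days. If nominal assignment is meant, the SAP needs to say so.

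Three other replies largely stand:
- **The rates are assumptions.** A reader might infer that about a third of all subjects will lose their SIE. The documents do not support that. Zero loss is possible, the top figures need visits spread evenly over their windows, and the 17–34% range also needs Visit 7 timed from Day 0.
- **Two-dose subjects may be rescued after dose 1** by the stool taken before dose 2. The SAP does not say whether it counts. The UAM1 Group 2 schedule, as it reads here, does not carry the same pre-vaccination mark, so this should be confirmed for the control.
- **UAM1 had the same timing.** A reader might infer a bias for or against the candidates. Nothing in the documents shows one: the collection rule is the same, and any difference in loss would depend on actual visit days in each study.

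The SAP's option to relax its missing-sample rule does not answer the point. It concerns the AUC's consecutive-missing rule and does not extend to the SIE.

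**Conclusion.** The mismatch is real and follows from the documents alone: a stool collected exactly as scheduled can fall on Day 24 or 25, and the written rule then makes the SIE missing. How often this happens cannot be known from the plan. On the stated assumptions it ranges from 0% to 30% of one-dose subjects. It is about half that in the pooled post-dose-1 comparison if the pre-dose-2 stool is used. After dose 2 it is 10–30% or 17–34% by the timing of Visit 7.

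The AUC effect is narrower than it may look. Visit 4 on Day 30 does not by itself cost the last point; the stool must also be taken only 1 day before.

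The consequence is lost precision in exploratory shedding endpoints, which are reported beside daily positivity, daily titres and time to cessation. No primary or secondary conclusion depends on it. Severity is minor, but the repair is cheap and best made before database lock.

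**What to change.** In SAP 6.7.1:
- Set the SIE Day 28 window to −4/+2 days (Days 24–30) after dose 1 and to Days 24–31 after dose 2. Keep ±2 days for Days 7, 14 and 21.
- Let no sample fill two slots. Where several qualify for Day 28, use the one closest to Day 28.
- State that the pre-vaccination stool on the day of dose 2 counts as a post-dose-1 sample.
- For the AUC, where the first sample after Day 21 falls on Days 29–31, use it to interpolate the curve to Day 28 instead of dropping it.
- Apply the same rules to UAM1.

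The cost is a few SAP sentences. The Day 28 value then spans a few more days, and curves that end on Days 24–27 keep their shorter length. The post-dose-2 window deliberately starts at Day 24. Reaching back to Day 22 would overlap the Day 21 window, so the small residual loss shown above is accepted.
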